**Do Not Dispense study drug if:**

- The patient is pregnant.
- No pregnancy tests were conducted for a FCBP.
- The patient states she did not use TWO reliable methods of birth control (unless practicing complete abstinence of heterosexual intercourse) [at least 28 days prior to treatment, during treatment, and during dose interruption].

1. I verified that the required pregnancy tests performed are negative.
2. I counseled FCBP regarding the following:
  - Potential risk of fetal exposure to lenalidomide: If lenalidomide is taken during pregnancy, it may cause birth defects or death to any unborn baby. Females are advised to avoid pregnancy while taking lenalidomide. The teratogenic potential of lenalidomide in humans cannot be ruled out. FCBP must agree not to become pregnant while taking lenalidomide.
  - Using TWO reliable methods of birth control at the same time or complete abstinence from heterosexual contact [at least 28 days prior to treatment, during treatment, during dose interruption and 28 days after discontinuation of lenalidomide].
  - That even if she has amenorrhea she must comply with advice on contraception

- Use of one highly effective method and one additional method of birth control AT THE SAME TIME. The following are examples of highly effective and additional effective methods of contraception:
  - Highly effective methods:
    - Intrauterine device (IUD)
    - Hormonal (birth control pills, injections, implants)
    - Tubal ligation
    - Partner's vasectomy
  - Additional effective methods:
    - Male condom
    - Diaphragm
    - Cervical Cap
- Pregnancy tests before, during, and after treatment, even if the patient agrees not to have reproductive heterosexual contact. Two pregnancy tests will be performed prior to receiving study drug, one within 10 to 14 days and the second within 24 hours of the start of study drug.
- Frequency of pregnancy tests to be done:
  - Every week during the first 28 days of this study and a pregnancy test every 28 days during the patient's participation in this study if menstrual cycles are regular or every 14 days if cycles are irregular.
  - If the patient missed a period or has unusual menstrual bleeding.
  - When the patient is discontinued from the study and at day 28 after study drug discontinuation if menstrual cycles are regular. If menstrual cycles are irregular, pregnancy tests will be done at discontinuation from the study and at days 14 and 28 after study drug discontinuation.
  - Stop taking study drug immediately in the event of becoming pregnant and to call their study doctor as soon as possible.
  - NEVER share study drug with anyone else.
  - Do not donate blood while taking study drug and for 28 days after stopping study drug.
  - Do not breastfeed a baby while participating in this study and for at least 28 days after study drug discontinuation.
  - Do not break, chew, or open study drug capsules.
  - Return unused study drug to the study doctor.
- 3. Provide Lenalidomide Information Sheet to the patient.

**FEMALE NOT OF CHILDBEARING POTENTIAL (NATURAL MENOPAUSE FOR AT LEAST 24 CONSECUTIVE MONTHS, A HYSTERECTOMY, OR BILATERAL OOPHORECTOMY):**

4. I counseled the female NOT of child bearing potential regarding the following:
  - Potential risks of fetal exposure to lenalidomide (Refer to item #2 in FCBP)
  - NEVER share study drug with anyone else.
  - Do not donate blood while taking study drug and for 28 days after stopping study drug.
  - Do not break, chew, or open study drug capsules
  - Return unused study drug capsules to the study doctor.

5. Provide Lenalidomide Information Sheet to the patient.

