**Schedule of Study Assessments: Arm A (Concurrent)**

Procedure	Screening	Cycle 1 & 2				Cycle 3	Cycle 4	Cycle 5	Cycle 6	Cycle 7+	End of Therapy o	Follow-Up p
		W1	W2	W3	W4							
Clinical Assessment												
Informed Consent	X											
Physical Examination a	X	X	X	X	X	X	X	X	X	X	X	X
ECOG Performance Status b	X	X	X	X	X	X	X	X	X	X	X	X
Concomitant medications	X	X	X	X	X	X	X	X	X	X	X	X
Interval infection history c		X	X	X	X	X	X	X	X	X	X	X
Record adverse events		X	X	X	X	X	X	X	X	X	X	
Perform Drug Accountability d	X	X	X	X	X	X	X	X	X	X		
Education and Counseling e		X				X	X	X	X	X		
Response assessment n						X		X		X n	X	X
Laboaratory Studies and Procedures												
ECG	X											
Complete blood count m	X	X	X	X	X	X	X	X	X	X	X	X
Serum chemistries f	X	X	X	X	X	X	X	X	X	X		X
Urinalysis	X											
Quantitative serum immunoglobulins	X					X		X		Every 6 mo	X q	X
Direct and indirect antiglobulin test	X											
TSH	X											X
Pregnancy testing g	X	X	X	X	X	X	X	X	X	X	X	
Bone marrow biopsy h	Optional											X
Risk stratification studies i	X											
CT scans r	X											
Anti-pneumococcal antibody titers		X				X		X	X			
Treatment												
Allopurinol l		X	X	X	X							
Thromboprophylaxis k		X	X	X	X	X	X	X	X	X		
Dispense Lenalidomide l		X				X	X	X	X	X		
Lenalidomide		X	X	X	X	X	X	X	X	X		
PCV13 administration						X		X				
Correlative Studies												
Pharmacokinetic Studies s			C2 D1,2									
Pharmacodynamic Studies t	X	C1 D1,3 C2 D1	C1 D8			X		X				

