### Schedule of Study Assessments: Arm B (Sequential)

Procedure	Screening	Cycle 1	Cycle 2	Cycle 3	Cycle 4 & 5				Cycle 6	Cycle 7+	End of Therapy o	Follow-Up p
					W1	W2	W3	W4				
Clinical Assessment												
Informed Consent	X											
Physical Examination a	X	X	X	X	X	X	X	X	X	X	X	
ECOG Performance Status b	X	X	X	X	X	X	X	X	X	X	X	
Concomitant medications	X	X	X	X	X	X	X	X	X	X	X	
Interval infection history c		X	X	X	X	X	X	X	X	X	X	
Record adverse events		X	X	X	X	X	X	X	X	X	X	
Perform Drug Accountability d	X				X	X	X	X	X	X	X	
Education and Counseling e					X				X	X	X	
Response assessment n					C5					X n	X	X
Laboaratory Studies and Procedures												
ECG	X											
Complete blood count m	X	X	X	X	X	X	X	X	X	X	X	X
Serum chemistries f	X	X	X	X	X	X	X	X	X	X	X	
Urinalysis	X											
Quantitative immunoglobulins	X	X		X	X					Every 6 mo	X g	X
Direct and indirect antiglobulin test	X											
TSH	X										X	
Pregnancy testing g	X				X g	X	X	X	X	X	X	
Bone marrow biopsy h	Optional										X	
Risk stratification studies i	X											
CT scans r	X										X	
Anti-pneumococcal antibody titers		X		X	X							
Treatment												
Allopurinol l					X	X	X	X				
Thromboprophylaxis k					X	X	X	X	X	X		
Dispense Lenalidomide l					X	X	X	X	X	X		
Lenalidomide					X	X	X	X	X	X		
PCV13 administration		X		X								
Correlative Studies												
Pharmacokinetic Studies s					C5 D1,2							
Pharmacodynamic Studies t	X	X			C4 D1,3 C5 D1	C4 D8			X			

- a. Physical examination should include vitals signs, weight, general physical examination (including neurologic examination), measurement of liver and spleen span in centimeters below the costal margin in the anterior axillary line, and bi-dimensional measurement of cervical, supraclavicular, axillary, and inguinal nodes.
- b. See [Appendix A](#).
- c. See [6.3.10](#) for required information to be documented for each episode of infection.
- d. Patient medication diary is reviewed to assess patient compliance on the first day of each cycle in which lenalidomide is administered.

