- e. The Lenalidomide Education and Counseling Guidance Document ([Appendix D](#)) must be completed and signed by a trained counselor at the participating site prior to each dispensing of lenalidomide treatment. A copy of this document must be maintained in the patient records. The Lenalidomide Information Sheet ([Appendix E](#)) will be given to each patient receiving lenalidomide treatment. The patient must read this document prior to starting lenalidomide study treatment and each time they receive a new supply of study drug.
- f. Serum chemistries should include: comprehensive metabolic panel, phosphate, uric acid, and LDH.
- g. Pregnancy tests for females of childbearing potential. A female of childbearing potential (FCBP) is a sexually mature female who: 1) has not undergone a hysterectomy or bilateral oophorectomy; or 2) has not been naturally postmenopausal (amenorrhea following cancer therapy does not rule out childbearing potential) for at least 24 consecutive months (i.e., has had menses at any time in the preceding 24 consecutive months). Pregnancy tests must occur within 10 – 14 days and again within 24 hours prior to initiation of lenalidomide. FCBP with regular or no menstruation must have a pregnancy test weekly for the first 28 days and then every 28 days while on study treatment (including breaks in treatment); at discontinuation of lenalidomide and at Day 28 post the last dose of lenalidomide. Females with irregular menstruation must have a pregnancy test weekly for the first 28 days and then every 14 days while on study treatment (including breaks in treatment), at discontinuation of lenalidomide and at Day 14 and Day 28 post the last dose of lenalidomide (see [Appendix C: Risks of Fetal Exposure, Pregnancy Testing Guidelines and Acceptable Birth Control Methods](#)).
- h. Unilateral bone marrow biopsy and aspirate will be obtained at end of treatment. In addition to routine pathology, aspirate samples should be studied for, interphase cytogenetics, standard CLL FISH panel, CpG stimulated karyotype, and flow cytometry. If patients decline bone marrow biopsy at end of study, these same studies should be done on peripheral blood. If patients demonstrate anti-ROR1 antibody response, a research bone marrow aspirate may be done every 6 months to isolate normal B-cells for correlative studies.

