#### **Before starting study drug**

##### *Female Patients:*

FCBP must have two negative pregnancy tests (minimum sensitivity of 25 mIU/mL) prior to starting study drug. The first pregnancy test must be performed within 10 to 14 days prior to the start of study drug and the second pregnancy test must be performed within 24 hours prior to the start of study drug. The patient may not receive study drug until the study doctor has verified that the results of these pregnancy tests are negative.

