#### **During study participation and for 28 days following study drug discontinuation**

##### *Female Patients:*

- FCBP with regular or no menstrual cycles must agree to have pregnancy tests weekly for the first 28 days of study participation and then every 28 days while on study, at study discontinuation, and at day 28 following study drug discontinuation. If menstrual cycles are irregular, the pregnancy testing must occur weekly for the first 28 days and then every 14 days while on study, at study discontinuation, and at days 14 and 28 following study drug discontinuation.
- At each visit, the Investigator must confirm with the FCBP that she is continuing to use two reliable methods of birth control.
- Counseling about pregnancy precautions and the potential risks of fetal exposure must be conducted at a minimum of every 28 days.
- If pregnancy or a positive pregnancy test does occur in a study patient, study drug must be immediately discontinued.
- Pregnancy testing and counseling must be performed if a patient misses her period or if her pregnancy test or her menstrual bleeding is abnormal. Study treatment must be discontinued during this evaluation.

- Females must agree to abstain from breastfeeding during study participation and for at least 28 days after study drug discontinuation.

*Male Patients:*

- Counseling about the requirement for complete abstinence or condom use during sexual contact with a pregnant female or a female of childbearing potential and the potential risks of fetal exposure to lenalidomide must be conducted at a minimum of every 28 days.
- If pregnancy or a positive pregnancy test does occur in the partner of a male study patient during study participation, the investigator must be notified immediately.

*Additional precautions*

- Patients should be instructed never to give this medicinal product to another person and to return any unused capsules to the study doctor at the end of treatment.
- Female patients should not donate blood during treatment and for at least 28 days following discontinuation of lenalidomide.
- Male patients should not donate blood, semen or sperm during treatment or for at least 28 days following discontinuation of lenalidomide.
- Only enough study drug for 28 days or one cycle of therapy (whichever is shorter) may be dispensed with each cycle of therapy.

**APPENDIX D                    LENALIDOMIDE EDUCATION AND COUNSELING GUIDANCE  
DOCUMENT**

Protocol Number: \_\_\_\_\_

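### Appendices C and D tie weekly pregnancy tests to the start of the study, which in Arm B is vaccine-only Cycle 1 and not the first lenalidomide cycle (Cycle 4)

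*Combined protocol and SAP*

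**What the plan says.** Appendix C, under the tests required during participation, says that a woman of childbearing potential whose periods are regular or absent "must agree to have pregnancy tests weekly for the first 28 days of study participation and then every 28 days while on study". With irregular cycles the later interval is 14 days. Appendix D, item 2, says "Every week during the first 28 days of this study and a pregnancy test every 28 days", again with 14 days for irregular cycles. Neither appendix distinguishes the arms.

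Footnote g of the study calendar (Section 10) says that such women "must have a pregnancy test weekly for the first 28 days and then every 28 days while on study treatment". It does not say what the 28 days are counted from, and it ends by referring the reader to Appendix C.

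The tests before the first dose are tied to the drug throughout. Footnote g requires a test 10 to 14 days beforehand "and again within 24 hours prior to initiation of lenalidomide". Appendix C says "The first pregnancy test must be performed within 10 to 14 days prior to the start of study drug", and Appendix D has "one within 10 to 14 days and the second within 24 hours of the start of study drug".

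Table 2 (Section 5.1.1) gives Arm B no lenalidomide in Cycles 1 to 3 and 2.5 mg/day in Cycle 4. In the Arm B calendar, the pregnancy-testing row is marked at screening, blank in Cycles 1 to 3, and marked in weeks 1 to 4 from Cycle 4.

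**The concern.** Weekly testing early in treatment is there to detect a pregnancy soon after exposure begins. The protocol treats lenalidomide as a possible human teratogen, so the weekly window should open with the first dose. In Arm B the appendices open it 84 days earlier, when no lenalidomide is being taken, and it has closed well before the drug starts.

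The wording is in working text. Under footnote e, a trained counselor completes and signs the Appendix D form before each dispensing. The form asks the counselor to confirm that the required tests were negative, and the same form states the frequency. In Arm B the form comes into use when lenalidomide is first dispensed, by which time the weekly window that it describes has passed. A counselor who relied on the form alone could accept fewer tests in the first month on drug than the calendar requires.

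**Working it through.** The protocol states no figure to reproduce. The check is a day count and a comparison of schedules.

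**Inputs**
- Cycle length: 28 days (Section 5.1.1).
- First lenalidomide cycle: Arm A Cycle 1, Arm B Cycle 4 (Table 2 and the text below it).
- Weekly window in the appendices: the first 28 days of the study; afterwards every 28 days, or every 14 if irregular.
- Weekly marks in the Arm B calendar: none in Cycles 1 to 3, weeks 1 to 4 from Cycle 4.

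**Position of the windows in Arm B**
- First lenalidomide dose: 3 × 28 + 1 = study day 85.
- First 28 days on drug (Cycle 4): days 85 to 112.
- Weekly window, appendices read literally: days 1 to 28.
- Distance between the two starts: 85 − 1 = 84 days. The windows do not overlap.

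In Arm A both readings give days 1 to 28, so there is no conflict.

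**Number of tests in Arm B**

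| Period | Calendar | Appendices, regular cycles | Appendices, irregular cycles |
|---|---|---|---|
| Cycle 1 (vaccine only) | 0 | 4 | 4 |
| Cycle 4 (first 28 days on drug) | 4 | 28/28 = about 1 | 28/14 = about 2 |

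**Largest added delay in detection during Cycle 4**
- Regular cycles: 28 − 7 = 21 days.
- Irregular cycles: 14 − 7 = 7 days.

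These delays arise only if a site follows the literal appendix instead of its calendar and no test is prompted by a missed period.

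**After the fix**

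Counted from the first lenalidomide dose, the weekly window is days 1 to 28 in Arm A (unchanged) and days 85 to 112 in Arm B. That agrees with the Cycle 4 marks in the Arm B calendar.

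**The case against.** The best defense is that the intended meaning can be recovered. In footnote g the weekly rule directly follows the sentence on starting lenalidomide, and it goes on to study treatment and its discontinuation; footnotes e and l also use study treatment to mean lenalidomide. With Cycles 1 to 3 blank in the Arm B calendar, the schedule there is reasonably clear. Appendix C moves from a section on the time before study drug to one on participation, so participation may be meant to begin with the drug. The Appendix D form is first used in Arm B around Cycle 4, where a reader could take its 28 days as the first 28 on drug.

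Much of this stands, and it is why the consequence is small. It does not remove the inconsistency. The appendices name the study, not the drug, as the starting point. In Arm B the two differ by 84 days, and footnote g sends the reader to Appendix C.

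Three stronger readings are tempting, and the documents do not support them.

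- *The grids require 56 days of weekly tests against 28 in footnote g.* Both grids merge the first two lenalidomide cycles into one block of weeks 1 to 4. Footnotes narrow those blocks elsewhere: allopurinol is required only through the first lenalidomide cycle (footnote j), blood counts are on Days 1 and 8 (footnote m), and dispensing is limited to one supply per cycle (footnote l), although Arm B marks all four weeks. Footnote g likewise sets the testing frequency.
- *The Arm B grid omits the test 10 to 14 days before lenalidomide.* That test falls on study days 71 to 75 (85 − 14 to 85 − 10), which are Cycle 3 Days 15 to 19, and Cycle 3 has no mark. But the Cycle 4 week 1 cell carries its own reference to footnote g, which requires the test. A Cycle 3 mark would be a matter of presentation.
- *Arm B women go without weekly testing on drug.* The calendar requires weekly tests from Cycle 4.

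**Conclusion.** The inconsistency is real and minor. For Arm B, Appendices C and D place the weekly tests on days 1 to 28, before any lenalidomide, while the calendar places them from day 85. In the first 28 days on drug the literal appendix wording gives about 1 test (regular cycles) or 2 (irregular), against 4 in the calendar.

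Several safeguards hold whichever text is followed: two negative tests before the first dose, two contraceptive methods or abstinence, and a test after a missed period or abnormal bleeding. The 21-day or 7-day delay is therefore a conditional worst case and not an expected effect. No endpoint or analysis is touched.

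The counts assume 28-day cycles without delays and a literal reading of the appendices. The number of women of childbearing potential in Arm B is not given. Section 9 says that few patients are still on treatment, so the practical effect at this version may be very small; the documents do not state whether enrolment is closed.

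**What to change.** In Appendix C, in Appendix D item 2 and, for consistency, in footnote g, write: *weekly for the first 28 days of lenalidomide treatment (Arm A: Cycle 1; Arm B: Cycle 4), then every 28 days (every 14 days if menstrual cycles are irregular) while on lenalidomide, including breaks in treatment*. Leave the tests before the first dose and at and after discontinuation as they are.

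The cost is one phrase in two appendices and one footnote, which can go into the next amendment. No test is added to the calendar schedule, and Arm A's weekly window does not change. A mark for the pre-lenalidomide test at Cycle 3 Days 15 to 19 in the Arm B grid is optional; it would show a test that footnote g already requires.

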**MALE:**

6. I counseled the Male patient regarding the following:
  - Potential risks of fetal exposure to lenalidomide (Refer to item #2 in FCBP).
  - To engage in complete abstinence or use a condom when engaging in sexual contact (including those who have had a vasectomy) with a pregnant female or a female of childbearing potential, while taking study drug, during dose interruptions and for 28 days after stopping study drug.
  - Males should notify their study doctor when their female partner becomes pregnant and female partners of males taking study drug should be advised to call their healthcare provider immediately if they get pregnant.
  - NEVER share study drug with anyone else.
  - Do not donate blood, semen or sperm while taking study drug and for 28 days after stopping study drug.
  - Do not break, chew, or open study drug capsules.
  - Return unused study drug capsules to the study doctor.

7. Provide Lenalidomide Information Sheet to the patient.

Counselor Name (Print): \_\_\_\_\_

Counselor Signature: \_\_\_\_\_ Date: \_\_\_\_ / \_\_\_\_ / \_\_\_\_

\*\*Maintain a copy of the Lenalidomide Education and Counseling Guidance Document in the patient records.\*\*

Celgene  
Corporation

**Celgene Pregnancy Prevention & Counseling Program  
Site Counselor Identification Form  
for NCI Studies**

**NCI Protocol #:** \_\_\_\_\_

Principal Investigator:

Institution Name:

- Please identify at least two (2) counselors and fax back to [contact]
- Use one form per counselor.
- Identified counselors must be licensed healthcare professionals (e.g. RN, PA, RPh, PhD, LPN, CNP, or MD) and must not be the principal investigator.
- If you have any questions, please email ([coop\\[contact]](mailto:[contact]))

Counselor Information		
CTEPpersonID: _____	CTEPsiteID: _____	
First Name: _____	Middle Initial: _____	Last Name: _____
License Type: (circle one)    MD    PhD    PA    CNP    RN    LPN    RPh    Other: _____		
Email Address: _____		
Phone: _____ Fax: _____		
Institution Street Address: _____		
City: _____ State/Region: _____		
Zip/Post Code: _____ Country: _____		
Previously approved as a Counselor?  No  Yes		
If no, please list all the protocols #(s), corresponding CTEPsiteID(s) and institution names(s) that you plan to provide counseling for:		
If yes, please list the protocols #(s), corresponding CTEPsiteID(s) and institution names(s) for protocols Celgene has already associated you with:		
Protocol#:	CTEPsiteID	Institution

